### **5.0 Number of Subjects**

The proposed single-site study will be conducted at The Ocular Surface Institute at the University of Houston College of Optometry. Up to 60 subjects will be screened for study inclusion, with the goal of completing 20 subjects. Subjects that screen fail may be rescreened for study inclusion up to 3 additional times at the discretion of the study investigator.

Currently, there is no information on the time from contact lens fitting to the development of LWE. This pilot study is designed to collect data which can be used to determine the sample size required to conduct a larger-scale clinical trial. It is anticipated that enrolling 20 subjects will approach the requirements of the central limit theorem for statistical analysis. Since the subjects in the study will be wearing FDA-approved contact lenses on a daily wear modality (i.e. not sleeping in contact lenses), the study does not present more than minimal risk to the subject and a power analysis is not required.

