## **8.0 Procedures Involved**

The study is a clinical trial. Twenty subjects who are either neophytes or experienced soft contact lens wearers who have not worn contacts for at least the past 7 days will be enrolled. Patients will be seen for 3 visits over a period of approximately 1 week. The pre-contact lens insertion assessment (Visit 1.1) will determine subject eligibility for the study and will take approximately 90 minutes. Subjects will then be released to a waiting room for a 2-hour waiting period. The 2-hour post contact lens fitting assessment (Visit 1.2) will take approximately 55 minutes. The 7 day post-insertion assessment (Visit 2) will take approximately 55 minutes.

Data from subject's routine medical care that is pertinent to the study (e.g. topical ophthalmic medications, oral medications, etc.) will be collected by querying the subject (see Step 1.1.3 below). This data will be considered subject source documentation and will be kept as part of the subject's study binder in a secure room in the Ocular Surface Institute (TOSI).

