### **23.0 Resources**

## **FULL PROTOCOL TITLE: The Impact of Contact Lens Coefficient of Friction (CoF) on the Development of Lid Wiper Epitheliopathy (LWE)**

The study team completed all necessary ethics training requirements. The co-PIs ([name], OD, PhD and [name], OD, PhD) have over a decade of clinical research experience conducting clinical studies and will oversee the other study personnel.

The number of subjects to be recruited is based on the typical number of subjects needed to approach the central limit theorem. With an abundance of contact lens wearers in the surrounding community, we believe that we should be able to complete enrollment within 3 months.

This study utilizes the clinics of The Ocular Surface Institute to see study subjects on the campus of the University of Houston.

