## **FULL PROTOCOL TITLE: The Impact of Contact Lens Coefficient of Friction (CoF) on the Development of Lid Wiper Epitheliopathy (LWE)**

### Addendum: Statistical Analyses

Statistical analyses were performed in SPSS v26 (IBM) and GraphPad. When data were not significantly different from a normal distribution (non-invasive tear break up time, tear meniscus height), statistical analyses were conducted using paired t-tests and repeated-measures analyses of variance (RM-ANOVA), with adjusted post-hoc t-tests, when appropriate. For NITBUT and TMH, the RM-ANOVA included two repeated factors—lens type (Acuvue Oasys and Air Optix Night and Day) and time (baseline, 2 hours post-fitting and 7 days after lens fitting). For data that was not normally distributed (LWE staining), Friedman and Mann-Whitney non-parametric statistics were performed. MMP concentrations were adjusted by multiplying raw values by the dilution factor. Tear film MMP concentrations under the level of detection (LOD) were divided by  $\sqrt{2}$  (Croghan et al. 2003). Outliers in MMP data sets were analyzed using the ROUT function in Graphpad Prism 8.4.1 and were removed prior to analysis.

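### N = 20 rests only on the central limit theorem, and no paired LWE difference, SD or interval is specified although the pilot is meant to inform a larger trial's size

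*Combined protocol and SAP*

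**What the plan says.** **Basis for the number.** Section 5.0 states: "It is anticipated that enrolling 20 subjects will approach the requirements of the central limit theorem for statistical analysis". Section 23.0 (Resources) says the number to be recruited is "based on the typical number of subjects needed to approach the central limit theorem". No other basis appears. Section 5.0 sets power aside because "the study does not present more than minimal risk to the subject and a power analysis is not required".

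**Purpose.** Section 5.0: "This pilot study is designed to collect data which can be used to determine the sample size required to conduct a larger-scale clinical trial".

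**Counts.** Section 5.0: "Up to 60 subjects will be screened for study inclusion, with the goal of completing 20 subjects". Section 8.0 also enrols twenty, so there is no allowance for dropout.

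**Design and hypotheses.** Section 1.0 puts one lens on each eye of the same subject, with the eye chosen at random. It states a non-directional hypothesis about LWE at 2 hours and another at 1 week. Section 7.0 makes LWE at those times the primary endpoint. Section 8.0 sets significance at p ≤ 0.05.

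**Analysis.** The protocol body names no test for the between-lens LWE comparison. The Addendum, written in the past tense, says that for data that were not normal (LWE staining) "Friedman and Mann-Whitney non-parametric statistics were performed". It describes paired t-tests and repeated-measures ANOVA for tear break-up time and tear meniscus height, which are not listed endpoints. The only estimate named for LWE is its correlation with tear MMP levels (Section 8.0).

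**The concern.** The central limit theorem describes how a sample mean behaves as n grows. It can support the use of a mean-based interval at a given n. It cannot show that n is large enough to detect or estimate anything, so 20 has no stated link to the question. Minimal risk to subjects does not supply that link either. Pilot status can excuse a power calculation, but a statement of precision would normally take its place.

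The stated analysis also fits the stated purpose poorly. Sizing a within-subject trial on LWE needs the between-lens difference and the spread of the paired differences. Friedman and Mann-Whitney return a test statistic and a p-value. Mann-Whitney also treats the two eyes of one subject as independent samples, which discards the main advantage of the contralateral design.

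At stake are the usefulness of the pilot's primary result for its stated purpose, and the sensitivity of the lens comparison.

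**Working it through.** **1. Can 20 be reproduced?** No. The documents give no effect size, SD, power or precision target, so there is no plan figure to check. The steps below ask what 20 pairs deliver. Inputs: n = 20 pairs (Section 5.0); alpha = 0.05 (Section 8.0), read as two-sided because the alternatives in Section 1.0 are non-directional. Results are in units of the SD of the paired LWE difference, which the documents do not give.

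**2. Precision of the mean paired difference.** Half-width of the 95% CI = t(0.975, 19)/√20 = 2.093/4.472 = 0.468 SD. If 18 or 15 subjects complete (assumed), it is 0.497 or 0.554 SD.

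**3. Detectable difference (paired-t benchmark).** Normal approximation at 80% power: (1.960 + 0.842)/√20 = 0.63 SD. The noncentral t gives 0.66 SD. Power by noncentral t for assumed standardised differences:

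| Difference (SD) | 0.2 | 0.3 | 0.5 | 0.8 |
|---|---|---|---|---|
| Power | 14% | 25% | 56% | 92% |

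**4. Precision of the SD (normal-theory benchmark).** The limits are √(19/χ²) times the observed SD: √(19/32.852) = 0.76 and √(19/8.907) = 1.46. A later trial's required N scales with SD², so for a fixed target difference it is uncertain by factors of 0.58 to 2.13.

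**5. Effect of ignoring the pairing.** This was simulated with 20 pairs and 4,000 trials per setting. Height and width were each graded 0–3 by cutting a normal variable at 0.2, 0.9 and 1.6, then averaged. The cut-points, the between-eye correlation and the shift of 0.6 latent SD are assumptions. Large-sample p-values were used.

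| Latent between-eye correlation | Mann-Whitney, no difference | Wilcoxon signed-rank, no difference | Mann-Whitney, shift | Wilcoxon signed-rank, shift |
|---|---|---|---|---|
| 0 | 5.2% | 5.5% | 63.0% | 61.0% |
| 0.5 | 1.2% | 4.9% | 66.5% | 84.1% |
| 0.8 | 0.2% | 5.0% | 72.0% | 98.8% |

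Entries are rejection rates at 0.05. When the two eyes are correlated, Mann-Whitney falls well below its nominal level and loses power. A Friedman test across the two lenses respects the pairing and rejected in 4.3% to 5.4% of trials with no difference. The Addendum does not say which of its two tests compares lenses and which compares times.

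**6. Is a mean difference defensible on these grades?** In simulations with assumed zero-heavy 0–3 grades (40–75% zeros, latent correlation 0.3–0.6, no shift or a 0.5 SD shift), the t interval from 20 pairs covered the true mean difference in 94–96% of trials. The chi-square limits for the SD did worse, covering 72–94%, and how far they fall short depends on the assumed shape. Step 2 is therefore reasonably robust in these settings, while step 4 tends to understate the uncertainty.

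**The case against.** The strongest reply is that this is a pilot with no earlier data on how fast LWE develops, so a power calculation had nothing to work from. The Addendum reports analyses already done, with rank tests tied to observed non-normality. That choice, made after the protocol, does not show that the protocol was inconsistent when written. Section 5.0 promises data and does not name an SD. All of this stands. It removes the charge of a missing power calculation, but not the absence of any precision statement or specified LWE estimate.

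Three stronger readings are tempting, and the documents do not support them.

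- A reader might infer that the theorem has no part in the analysis because LWE is ranked. Large-sample p-values for both rank tests rest on a limit theorem for rank sums, and the Addendum does not say whether exact or large-sample p-values were used. The mean-based analyses of tear break-up time and tear meniscus height also lean on it. The interval proposed here does so too, and step 6 suggests that 20 pairs serve it tolerably. The theorem still does not justify 20.
- A reader might infer that the larger trial will be left without its inputs. The choice of test destroys nothing: the paired difference and its SD can be computed from the same 20 pairs.
- A reader might infer that a non-significant result will be taken as no CoF effect. No section says so. The power figures in step 3 show only that such a reading would be unsafe.

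**Conclusion.** The point holds in a limited form. N = 20 has no basis that speaks to detection or precision. The analysis stated for the primary endpoint specifies no between-lens estimate, SD or interval, although sizing a later trial is the declared purpose. Mann-Whitney, if used to compare lenses, ignores the pairing of eyes.

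With 20 complete pairs, the mean difference is known to about ±0.47 SD. The 0.66 SD detectable difference and the 0.76–1.46 limits for the SD assume roughly normal differences and, for the former, a paired t-test. The Addendum calls LWE non-normal and uses other tests, so these are benchmarks and do not describe the power of the stated analysis. The loss from Mann-Whitney depends on the between-eye correlation, which the documents do not give; under the assumptions in step 5 it is nil at zero correlation and 18 to 27 percentage points at 0.5 to 0.8 (84.1 − 66.5 and 98.8 − 72.0).

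The fault lies in what is specified and reported. It does not invalidate the data or call for a different N.

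**What to change.** - At 2 hours and at 1 week, make the main LWE output the paired difference (high-CoF eye minus low-CoF eye) with its SD and 95% CI.
- Support it with a paired rank test, such as the Wilcoxon signed-rank test, in place of Mann-Whitney for the lens comparison. State which test addresses lens and which addresses time.
- If the central limit theorem sentences in Sections 5.0 and 23.0 are replaced, state a 95% CI half-width of about 0.47 SD for 20 complete pairs. Label the SD limits (0.76–1.46 times the estimate) and the 0.66 SD detectable difference as normal-theory, paired-t benchmarks.

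The cost is a small table of paired differences, some wording, and a justification that reads less favourably. No further subjects or measurements are needed. Because the Addendum describes completed analyses, the useful part is the added estimates and the paired test; rewording the rationale alone would change no result.

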### **6.0 Recruitment Methods**

Potential subjects will be recruited from the patients, students and staff of the University Eye Institute/University of Houston College of Optometry, as well as the surrounding community via verbal communication, print media (e.g. study fliers, newspaper adverts), telephone and electronic media (e.g email, The Ocular Surface Institute Website, social media). Additionally, potential subjects will be identified and recruited via The Ocular Surface Institute's research database.

The total duration of an individual subject's participation in the study will be approximately 1 week ( $\pm 2$  days). The study will consist of 3 visits on 2 days. Visit 1.1 will be a pre-fitting clinical assessment and contact lens fitting. Visit 1.2 will be a post contact lens insertion assessment completed approximately 2 hours after contact lens fitting in Visit 1.1. Visit 2 will be a 7 day ( $\pm 2$  days) post-contact lens fitting assessment for LWE. Expected visit timing is summarized in the table below:

Anticipated Visit Duration	
Study Visit	Duration
Visit 1.1: Baseline and Contact lens fitting	90 minutes
Approximately 2 hour waiting period	
Visit 1.2: 2-hour post contact lens insertion	55 minutes

## **FULL PROTOCOL TITLE: The Impact of Contact Lens Coefficient of Friction (CoF) on the Development of Lid Wiper Epitheliopathy (LWE)**

Visit 2: 1-week post contact lens fitting	55 minutes
---	------------

The anticipated duration to enroll and complete all study subjects is approximately 3 months. The estimated date for the investigators to complete primary analyses for this study is October, 2017.

## **7.0 Study Endpoints**

The primary study endpoints are as follows:

- Examine the development of LWE post-contact lens fitting at the following time points
  - 1-week post contact lens fitting
  - 2 hours after contact lens fitting

The secondary study endpoints are as follows:

- Examine the level of expression in ocular surface tear MMPs post-contact lens fitting at the following time points
  - Pre-contact lens fitting
  - 1-week post contact lens fitting
  - 2 hours after contact lens fit

## **8.0 Procedures Involved**

The study is a clinical trial. Twenty subjects who are either neophytes or experienced soft contact lens wearers who have not worn contacts for at least the past 7 days will be enrolled. Patients will be seen for 3 visits over a period of approximately 1 week. The pre-contact lens insertion assessment (Visit 1.1) will determine subject eligibility for the study and will take approximately 90 minutes. Subjects will then be released to a waiting room for a 2-hour waiting period. The 2-hour post contact lens fitting assessment (Visit 1.2) will take approximately 55 minutes. The 7 day post-insertion assessment (Visit 2) will take approximately 55 minutes.

Data from subject's routine medical care that is pertinent to the study (e.g. topical ophthalmic medications, oral medications, etc.) will be collected by querying the subject (see Step 1.1.3 below). This data will be considered subject source documentation and will be kept as part of the subject's study binder in a secure room in the Ocular Surface Institute (TOSI).

### Sequence of Events

## FULL PROTOCOL TITLE: The Impact of Contact Lens Coefficient of Friction (CoF) on the Development of Lid Wiper Epitheliopathy (LWE)

Note: Contact Lens wearing subjects should report to Visit 1 after discontinuing SCL wear for at least 7 days. Subjects should report to the visit wearing their habitual vision correction.

Visit 1.1: Screening, Enrollment and Baseline		
Step	Item	Details
1.1.1	Informed Consent	Review and complete the informed consent form
1.1.2	Subject Demographics	Collect subject demographic data
1.1.3	History	Collect subject history
1.1.4	Concomitant Medications	Collect information on concomitant medications
1.1.5	Habitual Contact Lens Information	For CL subjects, review habitual lens information and verify that they have discontinued lens wear for at least 7 days
1.1.6	Preliminary Review of Inclusion/Exclusion Criteria	Review Inclusion/Exclusion Criteria for subject study eligibility
1.1.7	Distance Visual Acuity	Perform Distance, High Contrast Visual Acuity using Snellen optotype, OD/OS with the patient's habitual correction.
1.1.8	Questionnaires: Ocular Surface Disease Index (OSDI)	All Subjects: Administer the OSDI 
 
• If OSDI scores is <math>\geq 23</math>; skip to 2.9, Final Evaluation
 

1.1.9	Auto-refraction	Perform auto-refraction and record the refractive error and keratometry readings
1.1.10	Oculus Keratograph	Perform the following procedures using Oculus Keratograph, OD/OS 
 
• Non-invasive Tear Break Up Time (NITBUT)
 
• Tear Meniscus Height
 

1.1.11	Phenol Red Thread	Perform Phenol Red Thread test without anesthesia, OD/OS.
1.22	Ocular Surface Tear Collection	Collect 10 $\mu$ L surface tears using a microcapillary tube.
1.1.12	Slit Lamp Exam with vital dye staining/LWE evaluation	Instill 1 drop of NaFL + Lissamine Green Combination Drop, wait 5 minutes, instill an additional drop, wait 1 minute, then evaluate slit lamp findings using the CCLRU grading scale and evaluate LWE

**FULL PROTOCOL TITLE: The Impact of Contact Lens Coefficient of Friction (CoF) on the Development of Lid Wiper Epitheliopathy (LWE)**

		
 
• If no LWE is observed in both eyes, skip to Step 2.9: Final Evaluation and discontinue the subject from the trial
 
• If LWE is observed in either eye, continue to Step 1.1.13: Digital Photography
 

1.1.13	Digital Photography	Perform Digital Photography of the Lid Wiper region OD/OS
1.1.14	Subjective Refraction	
Perform Manifest Refraction using maximum plus to best visual acuity.
 
 
• If the subject has <math>> 1.00\text{D}</math> refractive cylinder or greater than 1D of anisometropia, skip to Step 2.9: Final Evaluation and discontinue the subject from the trial
 

1.1.15	Subjective Spherical Equivalent Refraction	Perform Subjective Spherical Equivalent using maximum plus to best visual acuity.
1.1.16	Contact Lens Fitting	
Fit subject in contact lenses based upon the randomization schedule. Initial base curve should be selected as indicated in the fitting guide for each lens.
 
 
• If an acceptable contact lens fit cannot be obtained in either eye, skip to Step 2.9: Final Evaluation and discontinue the subject from the trial
 

1.1.17	Contact Lens Over-Refraction	Perform spherical over-refraction using maximum plus to best visual acuity
1.1.18	Contact Lens Power Adjustment (if necessary)	Modify contact lens power, based upon the Contact Lens Over-Refraction, if the subject gains 3 or more letters acuity
1.1.19	2 hour Waiting Period	Subjects released to waiting area for 2 hours

**FULL PROTOCOL TITLE: The Impact of Contact Lens Coefficient of Friction (CoF) on the Development of Lid Wiper Epitheliopathy (LWE)**

Visit 1.2 Note: Visit should be performed approximately 2 hours after lens insertion		
1.2.1	Visual Performance	Perform logMAR visual acuity
1.2.2	Oculus Keratograph	Perform the following procedures using Oculus Keratograph with the contact lens on eye, OD/OS 
 
• Non-invasive Tear Break Up Time (NITBUT)
 
• Tear Meniscus Height
 
• Video Contact Lens Fit
 

1.2.3	Ocular Surface Tear Collection	Collect 10µL surface tears using a microcapillary tube.
1.2.4	Contact Lens Removal	Remove the contact lenses and store in solution
1.2.5	Slit Lamp Exam with vital dye staining/LWE evaluation	Instill 1 drop of NaFL + Lissamine Green Combination Drop, wait 5 minutes, instill an additional drop, wait 1 minute, then evaluate slit lamp findings using the CCLRU grading scale and evaluate LWE
1.2.6	Contact lens Insertion and Removal Training and Dispense Contact Lens Solution	For Contact Lens Neophytes 
 
• Train on Insertion and Removal of contact lenses
 
 For all subjects 
 
• Educate subject on the proper use of the contact lens care solution
 

1.2.7	Exit Visual Acuity	Perform Distance, High Contrast Visual Acuity using Snellen optotype with the patient's habitual correction or contact lenses.

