## FULL PROTOCOL TITLE: The Impact of Contact Lens Coefficient of Friction (CoF) on the Development of Lid Wiper Epitheliopathy (LWE)

Visit 2: 1-Week Follow Up ( $\pm 2$ days) Note: Subjects should report to Visit 2 wearing their study assigned soft contact lenses.		
2.1	History	Collect subject history, compliance and reported wearing time
2.2	Visual Performance	Perform logMAR Visual Acuity
2.3	Questionnaires	Administer the OSDI to the subject
2.4	Oculus Keratograph	
Perform the following procedures using Oculus Keratograph (lens on eye for CL patients, bare eye for non-CL patients, OD/OS)
 
 
• Non-invasive Tear Break Up Time (NITBUT)
 
• Tear Meniscus Height
 
• Video Contact Lens Fit
 

2.5	Ocular Surface Tear Collection	Collect 10 $\mu$ L surface tears using a microcapillary tube.
2.6	Contact Lens Removal	Remove the contact lenses and store in solution
2.7	Slit Lamp Exam with vital dye staining/LWE evaluation	Instill 1 drop of NaFL + Lissamine Green Combination Drop, wait 5 minutes, instill an additional drop, wait 1 minute, then evaluate slit lamp findings using the CCLRU grading scale and evaluate LWE
2.8	Digital Photography	Perform Digital Photography of the Lid Wiper region OD/OS
Final Evaluation		
2.9	Exit Visual Acuity	Perform Distance, High Contrast Visual Acuity using Snellen optotype with the patient's habitual correction.
2.10	Final Evaluation Form	Complete the final evaluation form and indicate if the subject successfully completed the study
2.11	Protocol Deviations	Ensure any protocol deviations have been recorded

The procedures involved in the study are common clinical procedures found in Optometry/Ophthalmology. LWE assessment will occur following installation of sodium fluorescein and lissamine green ophthalmic drops. The upper and lower lids will be photographed using a slit-lamp biomicroscopy and a camera.

Photographs will be de-identified and graded subjectively for LWE using the Korb scale (see below). Photos may also be analyzed for objective LWE grading using custom coding in MATLAB.

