## FULL PROTOCOL TITLE: The Impact of Contact Lens Coefficient of Friction (CoF) on the Development of Lid Wiper Epitheliopathy (LWE)

Korb LWE Grading				
Grading	Description	Height (%)	Width (mm)	Final score (grade)
0	no LWE	<25	<2	<0.25
1	mild LWE	25-50	2-4	0.25-1.00
2	moderate LWE	50-75	5-9	1.25-2.00
3	severe LWE	>75	>10	2.25-3.00

\*Final LWE score is the average of the LWE Height and Width

The tears collected by capillary tubes will be stored at -80°C until luminex multibead analysis. 15 µg of total protein will be analyzed for matrix metalloproteinases (MMP)-1, -2, -7, -9, -10. Pre- and post-contact lens wear concentrations of MMP will be compared for each subject. MMPs are a family of zinc proteases and an increase in MMP expression occurs in response to a wide range of stimuli, including adhesion molecules, growth factors, cytokines and hormones and is associated with ocular surface damage. The correlation coefficient, r, will be determined between LWE and the tear film levels of MMPs.

A  $p \leq 0.05$  will be considered statistically significant.

Layman's Description of Procedures	
Patient demographics	The subjects will be asked questions about their age, sex, race and ethnicity.
History	The subjects will be asked questions about their systemic health, ocular disease and surgical history.
Concomitant Medications	The subjects will be asked questions about their current ocular and systemic medications.
Habitual Contact Lens Information	The subjects will be asked questions about how they use their current contact lenses, such as their current contact lens brand and wear time, as performed during a normal eye exam.
Auto-refraction	A machine will shine light into a subject's eye and will estimate their prescription using different powered lenses without making contact with the eye.
Oculus Keratograph	A machine uses a video camera to determine how long it takes for a subject's tear film to

**FULL PROTOCOL TITLE: The Impact of Contact Lens Coefficient of Friction (CoF) on the Development of Lid Wiper Epitheliopathy (LWE)**

	evaporate and the height of the pooled tears between the lower lid and the ocular surface without making contact with the eye.

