Phenol Red Thread	A small thread containing a pH indicator that turns from red to yellow when it contacts tears will be placed at the subject's lower lid margin and left for 15 seconds. The length that the tears have traveled will be measured. This test does not require anesthesia.
Slit Lamp Exam	A specialized microscope is used to shine light on the eye and to examine the health of the eyelids and the front of the eye.
Subjective Refraction/Spherical Equivalent Refraction	The subject's prescription is determined by placing different power lenses in front of the subject's eye, according to the subject's responses.
Contact Lens Fitting	A contact lens is placed on the eye and the fit is assessed (how much it moves, where it sits on the eye, etc.). This is done using a slit lamp biomicroscope.
Contact Lens Over-Refraction and Power Adjustment	Lenses will be placed in front of the subject's eye while wearing the study contact lenses to determine if the prescription needs to be changed according to the subject's responses. The contact lens power will be adjusted if needed.
Questionnaire: Ocular Surface Disease Index (OSDI)	The questionnaire asks the subject's vision during various tasks, eye pain, comfort in various environments, etc.

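### The baseline tear sample follows the Phenol Red Thread test and the post-fit samples do not, so any thread effect falls on one side only of the pre/post MMP comparison

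*Combined protocol and SAP*

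**What the plan says.** Section 7.0 lists tear MMP expression as the only secondary endpoint, at pre-fit, 2 hours and 1 week. Section 8.0, in the text after the Korb grading table, commits to a within-subject contrast: "Pre- and post-contact lens wear concentrations of MMP will be compared for each subject". It also plans a correlation between LWE and MMP levels.

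The Sequence of Events in section 8.0 sets the order of procedures:

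- **Visit 1.1.** Keratograph (1.1.10), then "Perform Phenol Red Thread test without anesthesia, OD/OS" (1.1.11), then the row headed "Ocular Surface Tear Collection" (printed as 1.22), then dye and slit lamp (1.1.12).
- **Visit 1.2.** Step 1.2.2 reads "Perform the following procedures using Oculus Keratograph with the contact lens on eye, OD/OS". Step 1.2.3 follows: "Collect 10µL surface tears using a microcapillary tube". The lens comes out at 1.2.4.
- **Visit 2.** Keratograph (2.4), tear collection (2.5), lens removal (2.6).

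The lay description of procedures says that the thread "will be placed at the subject's lower lid margin and left for 15 seconds" and takes up tears over that time. The statistical addendum describes how MMP values were scaled, how values below the detection limit were handled and how outliers were removed. It mentions no adjustment for the difference in collection order.

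**The concern.** A pre/post comparison within subjects is sound when the two samples are taken in the same way apart from the exposure. Here the pre-fit sample is drawn from a tear film that a thread has just contacted and partly absorbed, and the post-fit samples are not. If the thread changes tear volume or composition at all, that change is aligned with the contrast being tested. Pairing removes stable differences between subjects, but it does not remove a shift that occurs in every subject at baseline and at no other time.

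What is at stake is the per-subject MMP comparison. A baseline artefact could look like a response to lens wear, or could hide one. Section 5.0 says that the pilot is meant to inform the sample size of a larger trial, so a distorted MMP change could also carry forward if it were used for that purpose.

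**Working it through.** **1. Is the row printed 1.22 the baseline collection?** Yes, on any reasonable reading. It sits in the Visit 1.1 table between 1.1.11 and 1.1.12, Visit 1.2 has its own collection step (1.2.3), and section 7.0 lists a pre-fit MMP time point. The odd number looks like a numbering slip.

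**2. What precedes each sample?**

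| Sample | Step directly before | Thread test at this visit | Lens on eye |
|---|---|---|---|
| Pre-fit (1.22) | Phenol Red Thread, both eyes | Yes | No |
| 2 hours (1.2.3) | Keratograph | No | Yes |
| 1 week (2.5) | Keratograph | No | Yes |

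The thread is the immediate predecessor of the pre-fit sample only, and no interval between the two is stated.

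**3. How large could the consequence be?** The plan has no figure to reproduce. It gives no MMP mean, SD, thread effect or power calculation. The following is an illustration, not an estimate.

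- From the documents: 20 completers (section 5.0) and a significance level of 0.05 (section 8.0).
- Assumed: a two-sided paired t-test on log MMP (the addendum names no test specifically for MMP, and the plan does not state sidedness), no true change, baseline concentration lowered by a fraction d, and SD of the log change s.

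Formulas: standardised shift = −ln(1−d)/s; noncentrality = shift × √20; rejection probability from the noncentral t with 19 degrees of freedom and critical value 2.093.

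Example: d = 0.10 and s = 0.5 give 0.105/0.5 = 0.21, then 0.21 × 4.47 = 0.94, and a rejection probability of about 15%.

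| Baseline lowered by | −ln(1−d) | s = 0.3 | s = 0.5 | s = 1.0 |
|---|---|---|---|---|
| 5% | 0.051 | 11% | 7% | 5.5% |
| 10% | 0.105 | 32% | 15% | 7% |
| 20% | 0.223 | 88% | 47% | 16% |
| 30% | 0.357 | 99.9% | 86% | 33% |

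The apparent post/pre ratio with no true change is 1/(1−d): 1.05, 1.11, 1.25 and 1.43 for the four rows. The nominal rate is 5%. A thread effect that raised baseline concentration would bias the comparison the other way.

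**4. Does the assay cancel it?** Section 8.0 fixes the input at 15 µg of total protein. If the thread only diluted the tears, so that MMP and total protein fell together, equal protein loading could cancel the effect. It would not cancel a change in MMP relative to total protein. The addendum also multiplies raw values by a dilution factor. If that factor differs by sample, the scaling may restore a per-volume concentration and undo the offset; if it is one constant, it does not. The documents do not say which.

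**5. What is not affected?** The thread goes into both eyes, so a shared effect largely drops out of a comparison between the two lenses. LWE grading does not use the tear samples, so this point does not touch the primary endpoint.

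**The case against.** The strongest objection is that the documents show a difference in procedure and not a bias. Nothing in them says that a thread dilutes MMP or provokes reflex tearing. Section 11.0, in naming procedures that may cause mild discomfort, lists slit lamp, Keratograph, tear collection and dyes, but not the thread. This stands. A reader might infer that baseline is diluted and that MMP will therefore appear to rise after lens wear. The documents do not support that direction, or any particular size. The rejection rates follow entirely from the assumed shift and SD, and at 5% with s = 1.0 the effect is negligible.

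A reader might also infer that the dilution-factor scaling defeats the protein-load offset. That holds only if the factor is specific to each sample, which the addendum does not state.

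A third objection is that reordering does not make the three samples alike. That is correct. Post-fit tears are collected with the lens on the eye, and the Visit 1.2 sample follows the dye and the thread used earlier the same day. It would be wrong to claim that, after the change, all tears precede any thread or dye. But the lens is the exposure under study, whereas the thread directly before the baseline sample is an avoidable extra.

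Finally, this is a pilot and its stated hypotheses concern LWE between lenses. That limits the weight of the point, but the per-subject MMP comparison is still planned.

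**Conclusion.** The concern holds in a limited form. The order of procedures differs between the pre-fit sample and both post-fit samples, the difference is aligned with the planned pre/post MMP contrast, and no adjustment is described. Direction and size are unknown. Over the assumed range (5% to 30% lowering, log-change SD 0.3 to 1.0, paired t-test, 20 subjects) the false-positive rate runs from about 5.5% to above 99%. A range that wide shows only that the issue cannot be dismissed as harmless, not that it is large. Fixed protein loading may offset simple dilution.

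The conclusion rests on reading the table order as the order of performance and the row printed 1.22 as the baseline collection. It is confined to the pre/post MMP comparison, and to the LWE–MMP correlation only if that correlation uses pre-fit values or change from them, which the plan does not say.

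**What to change.** At Visit 1.1, collect tears after the Keratograph and before the Phenol Red Thread test, and correct the step number. The step immediately before collection then matches at all three time points. The cost is two rows exchanged. The thread reading would follow a 10 µL collection and may be lower, but it is not an endpoint in section 7.0 and section 3.0 ties no eligibility cut-off to it.

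Acknowledge the two differences that remain: the lens is on the eye at both post-fit collections, and the 2-hour sample follows the dye and thread used earlier that day. State also whether the dilution factor in the addendum is constant or specific to each sample.

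The addendum is written in the past tense, so the samples have probably been taken already. In that case, report the difference in collection order as a limitation of the pre/post MMP comparison and put the weight on between-lens contrasts at each post-fit visit. This needs tears collected and assayed separately for each eye. The collection rows, unlike those for the thread and the Keratograph, do not specify OD/OS, so confirm this first. The cost is a short statement in the report and less emphasis on the pre/post result.
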